Research with civilian samples also has shown that mindfulness is effective in decreasing anger and aggression. For example, Robbins et al. (2012) examined the effectiveness of a multi-session mindfulness treatment using a community sample and found that participation resulted in significant decreases in aggressive anger expression and difficulties regulating emotions, in addition to increases in trait mindfulness and self-compassion. Using a sample of court-referred women with alcohol abuse/dependence and aggression problems, Wupperman et al. (2012) found that a mindfulness intervention was effective in not only decreasing aggression, but also alcohol and drug use.

One of the most popular and well-researched interventions is Mindfulness Based Stress Reduction (MBSR) developed by Jon Kabat-Zinn (1990). MBSR is a group-based program designed for use with individuals experiencing a wide range of physical and mental health problems and focuses on teaching mindfulness meditation as well as mindfulness of everyday activities and emotional states. Studies examining the effectiveness of MBSR have found it to be effective in ameliorating a wide range of medical and mental health diagnoses (Baer, 2003). However, to our knowledge, only one study has examined the effectiveness of MBSR in decreasing anger and aggression (Robbins et al., 2012). To date, no researchers have examined the effectiveness of MBSR in decreasing anger and aggression among veterans with PTSD.

Mechanisms of Action of Mindfulness Treatment. One of the ways in which mindfulness is believed to exert its effects is by increasing one's ability to tolerate and regulate difficult emotions (Holzel et al., 2011). This is relevant to PTSD and aggression, given evidence linking emotion regulation difficulties to PTSD (Tull et al., 2007) as well as to the perpetration of aggression (Shorey et al., 2011). In addition, mindfulness has been shown to decrease physiological arousal and stress reactivity as indicated by reductions in heart rate and skin conductance levels (e.g., Campbell-Sills et al., 2006; Delizonna, Williams, & Langer, 2009; Goleman & Schwartz, 1976). Taken together, mindfulness may decrease the potential for an individual with PTSD to become angry and to engage in aggressive behavior by decreasing associated physiological reactivity and helping one regulate difficult emotions in response to stress.

Use of Experimental Procedures to Elicit Physiological Reactivity and Assess Aggression.

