Participants:

[figure not shown]
Inclusion Criteria: We will enroll 60 veterans with PTSD. To be eligible for the study, participants must meet current DSM-V diagnostic criteria for PTSD (American Psychiatric Association, 2013). PTSD will be established by interview using the Clinician Administered Posttraumatic Stress Disorder Scale for the DSM-V (CAPS-5; Weathers et al., 2013a). Participants must also indicate current difficulties with anger and aggression as indicated by a score of 20 or higher on the trait anger scale of the State Trait Anger Expression Inventory-2 (STAXI-2, Spielberger, 1999), indicating moderate to severe anger problems. Veterans from all eras will be eligible to participate.

Exclusion Criteria: Participants with a current diagnosis of bipolar disorder, psychotic disorder, or current substance use disorder with severe symptoms. Participants also must not have a seizure disorder and must not be taking any medications that would affect cognition or behavior on the aggression task, including pain medication, benzodiazepines, or antipsychotics. Participants also must not have a positive drug (e.g., amphetamine, opiates, and cocaine) or alcohol urine screen at the post-treatment session (see below), as these substances could affect performance on the study tasks implemented at that session. Finally, participants must not currently be receiving concurrent individual therapy or group therapy focused on anger and aggression and must not currently be participating in the modified TREC group offered at the West Haven VA (WHVA).

Research Design and Methods

For an overview of the time line for study procedures, see Figure 2.

Figure 2. Timeline of Study Procedures

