Trauma Scripting Procedure. After completing the diagnostic interviews (CAPS-5/SCID-5-RV), eligible participants will participate in a trauma-script development procedure as part of a well-validated, script-driven trauma imagery task (Pitman et al., 1987). For this procedure, participants will be asked to identify their most traumatic experience. If they identify more than one event, they will be asked to choose the one that they consider the most distressing. They will first be asked to describe the experience in writing using a script preparation form and then will be asked to indicate which of several different subjective visceral and muscular reactions (e.g., heart beating slower/faster, feeling sweaty, stomach in knots, feeling warm, hands trembling, tension in arms, nausea) may have accompanied the experience. Participants’ written responses will then be reviewed and they will be asked to clarify or expand on the details if necessary. After the session, a script lasting approximately 60 seconds in duration will be composed that portrays the traumatic experience in the second person, present tense, and incorporates the different visceral or muscular reactions. The script will then be audio recorded for playback

during the experimental portion of the post-treatment session. A research assistant (who will be named later upon being hired) will read the narrative scripts to be audio-recorded.

During this baseline session, participants will also complete a battery of self-report questionnaires (see below for full details) to assess baseline levels of anger and aggression.

Randomization Procedures. After participants have completed the Baseline Screening and Evaluation Session they will be randomized to either the TREC group or the MBSR group. To decrease the amount of time participants have to wait before starting group treatment, randomization will be implemented at the group level. That is, after 6 participants are recruited, they will be randomly assigned using urn randomization procedures, to either the TREC group or the MBSR group.

Post-treatment Session: After all participants have completed their assigned interventions (TREC or MBSR) they will be scheduled for the post-treatment session to be held in the biological studies laboratory at the WHVA. At this session, all participants will complete a battery of self-report questionnaires to assess post-treatment levels of anger and aggression (see below).

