To the extent that participants are experiencing any remaining distress as a result of their trauma exposure, the experimenter will work with the participant to assist them in returning to baseline levels of functioning. Finally, before ending the study appointment, participants will be informed that they will be contacted between 48-72 hours and then again one-week after their participation to follow-up about any negative reactions they may have had as a result of this portion of the session.

At the end of the post-treatment session, participants will be scheduled for a follow-up session to take place approximately 3 months after the post-treatment session to be held at the WHVA.

Follow-up Session. At this session, all participants will complete a similar assessment battery as was completed at the baseline and post-treatment sessions to assess any changes in levels of anger and aggression that may have occurred over the previous 3 months.

Drug and Alcohol Screening

At the beginning of the post-treatment session, participants will be asked to provide a urine sample to test for urine toxicology. If participants test positive on urine toxicology exams, we will encourage these individuals to maintain abstinence and they will be rescheduled. We will offer brochures for local substance use treatment facilities as appropriate. The extent to which participants are experiencing any symptoms of withdrawal will also be determined using the Clinical Institute Withdrawal Assessment for Alcohol Scale (CIWA-Ar; Sullivan et al., 1989). If participants indicate that they are experiencing any symptoms of withdrawal, they will be asked to reschedule their appointment at a later date. We will provide referrals to appropriate primary

care providers as appropriate.

Compensation

Participants will be compensated for their time and inconvenience while taking part in study procedures. Participants will be paid \$100 for the baseline and post-treatment sessions, and \$50 for the follow-up session. Participants also will be paid \$20 for completing questionnaires during week 3 and week 6 of treatment (for a total of \$40). Participants will not be paid for their participation in the TREC or MBSR intervention.

Assessments: See Table 1 for a listing of the primary assessments used in the current study.

Table 1. Schedule of Assessments

| | Baseline | 3-week | 6-week | Post-Treatment | 3-month Follow-up |
|--|----------|--------|--------|----------------|-------------------|

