Primary Aim 1 Hypothesis 1.1: Participants assigned to MBSR will report decreased levels of self-reported anger and aggression at post-treatment and at the 3-month follow up compared to those assigned to the TREC group. Scores on the State Trait Anger Expression Inventory-2 and the Buss-Perry Aggression Questionnaire will be used as the primary outcome variables for self-report anger and aggression. Intent-to-treat analyses will be conducted for these outcomes, which will be examined separately. Bonferroni adjustments will be implemented to control for Type 1 error. These data will be analyzed using mixed effects models with treatment, time, and treatment x time interaction as fixed effects. Subject will be the clustering factor and it will be nested within therapy group which will also be considered random. Different variance-covariance structures will be considered and the best one selected based on Schwartz’ Bayesian Information Criterion (BIC). Mixed effects models are the preferred method for analyses of such data as they use all available data on an individual, give unbiased results under general missing data assumptions and provide flexibility in modeling the correlation structure within subject. Significant interactions will be examined further using post-hoc tests.

Primary Aim 1, Hypothesis 1.2: Participants assigned to MBSR will exhibit lower levels of anger and aggression on the TRT compared to those assigned to the TREC group. Mixed effects models will be used to compare the TREC group to the MBSR group on responses on the TRT: (1) mean shock level across the TRT, and (2) total number of “20” shocks chosen on the TRT following the same strategy as for primary aim 1 hypothesis 1.1.

Secondary Aim 1, Hypothesis 1.1: Those assigned to MBSR will exhibit significant decreases in HR and SCL and increases in emotion regulation compared to those assigned to the TREC group. Mixed effects models will be used to compare the TREC group to the MBSR group on physiological variables (HR, SCL) and emotion regulation (DERS-S) following the same strategy as for primary aim 1, hypothesis 1.1.

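### The post-treatment urine screen is listed as an exclusion criterion although it falls after randomisation; the screening section reschedules instead, with no end point, so outcomes measured only at that visit can be lost

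*Combined protocol and SAP*

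**What the plan says.** - **Participants, Exclusion Criteria:** "Participants also must not have a positive drug (e.g., amphetamine, opiates, and cocaine) or alcohol urine screen at the post-treatment session". The reason given is "as these substances could affect performance on the study tasks implemented at that session". The entry points forward to a later section.
- **Randomization Procedures:** the stated timing is "After participants have completed the Baseline Screening and Evaluation Session they will be randomized to either the TREC group or the MBSR group", so allocation comes before any treatment.
- **Post-treatment Session:** this visit, by contrast, follows treatment: "After all participants have completed their assigned interventions (TREC or MBSR) they will be scheduled for the post-treatment session".
- **Drug and Alcohol Screening:** urine is taken at the start of the post-treatment session. "If participants test positive on urine toxicology exams, we will encourage these individuals to maintain abstinence and they will be rescheduled". Participants with withdrawal symptoms are also asked to come back later. The section gives no maximum number of attempts, no window for the delayed visit, and no rule for a participant who never screens negative.
- **Table 1:** the TRT is a primary outcome and is taken at post-treatment only. Heart rate (HR), skin conductance (SC) and DERS-S are also post-treatment only. STAXI-2 and BPAQ are taken at baseline, weeks 3 and 6, post-treatment and 3 months.
- **Debriefing (closing text):** the 3-month visit is booked at the end of the post-treatment session and timed from it.
- **Data Analyses, Primary Aim 1, Hypothesis 1.1:** "Intent-to-treat analyses will be conducted for these outcomes", meaning STAXI-2 and BPAQ, by mixed models on all available data. Hypothesis 1.2 applies the same strategy to the TRT.

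**The concern.** Eligibility should be settled before allocation. This criterion can be checked only after allocation and a course of treatment, so applying it would condition the comparison on something treatment may have changed. The Background gives a reason to think it might: it reports a mindfulness intervention that "was effective in not only decreasing aggression, but also alcohol and drug use". If the arms differ in how often participants screen positive, those remaining are no longer the groups that were randomised.

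The outcomes taken only at this visit are the most exposed, and one of them is primary. The pilot's stated purpose adds to the stake: under Sample Size and Power Considerations, its effect sizes, including those for HR, SC and emotion regulation from this session, are to inform the size of a larger trial.

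**Working it through.** The documents give no positive-screen rate, dropout rate, effect size or SD, so there is no planned figure to reproduce. The main check sets the sections side by side.

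**1. Order of events.** Baseline, randomisation, intervention, post-treatment session, urine screen at its start. The criterion is therefore observed after randomisation and treatment.

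**2. Action on a positive screen.** The Exclusion Criteria imply the person is not eligible. Drug and Alcohol Screening says the person is rescheduled. The first, taken literally, conflicts with intent-to-treat. The second does not, but it has no end point.

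**3. A participant who never screens negative, under the rescheduling rule.**

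| Measure | Occasions in Table 1 | Left for this participant |
|---|---|---|
| TRT (primary) | post-treatment | none |
| HR, SC, DERS-S (secondary) | post-treatment | none |
| STAXI-2, BPAQ (primary) | five | baseline, weeks 3 and 6; post-treatment delayed or lost; 3 months at risk, because it is booked at the end of the missed session |

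A mixed model can use the earlier STAXI-2 and BPAQ values under missing-at-random. It has no other TRT, HR, SC or DERS-S value to use, so those comparisons become complete-case.

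**4. Reach of the rule against its reason.** The reason concerns task performance. The rule as written defers the person, with no provision for completing the questionnaires that day.

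**5. Size, for scale only.** All rates and gaps here are assumptions. If a fraction e of an arm is lost, and those lost score g SD above those kept, the mean of those kept lies e × g below the full-arm mean. With the same g in both arms:

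bias = (difference between arms in e) × g

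- Lower: (0.20 − 0.10) × 0.5 = 0.05 SD
- Upper: (0.20 − 0.10) × 0.8 = 0.08 SD

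The arm that loses more looks less aggressive than it is. With an assumed 30 per arm, 20% and 10% are 6 and 3 people, leaving 24 + 27 = 51. Ignoring clustering, the standard error of a difference at 30 per arm is √(1/30 + 1/30) = 0.26 SD, so the bias is about 0.2 to 0.3 of one standard error.

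A second model assumes no true effect and removes those with the highest substance-use liability, which correlates r with aggression. The mean of those kept is −r × φ(c)/(1 − e), where φ is the standard normal density and c its 1 − e quantile. The ratio φ(c)/(1 − e) is 0.195 for e = 0.10 and 0.497 for e = 0.30. Losing 10% of MBSR and 30% of TREC gives (0.497 − 0.195) × r, which is 0.06 SD at r = 0.2 and 0.15 SD at r = 0.5, against MBSR. Equal loss in both arms gives zero.

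**The case against.** The strongest reply is that the exclusion entry refers forward, gives a reason confined to the laboratory tasks, and is resolved by the screening section, which says reschedule. On that reading the screen is a condition for running the visit, filed under the wrong heading. This largely stands. A reader might infer that the plan removes randomised participants from analysis, but no section withdraws anyone or drops anyone from a dataset because of the screen. The reply does not supply an end to rescheduling or a rule for the person who never screens negative.

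Three further inferences are tempting and unsupported:

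- **That positive screens are likely because only severe substance use disorder is excluded.** Current users of pain medication, benzodiazepines or antipsychotics are excluded too, and no rate is given.
- **That those who stop treatment get no post-treatment visit.** The Post-treatment Session text ties scheduling to completion but speaks of all participants, and the Overview has all participants attend both later visits. The plan is silent on non-completers; it does not exclude them.
- **That the self-report intent-to-treat analysis fails.** A positive screen alone leaves a participant's other STAXI-2 and BPAQ values in the model.

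It is also fair to say that any bias may be small beside sampling error in a 60-person pilot. If mindfulness does reduce substance use, TREC would lose more people and the bias would run against MBSR. That direction is itself an assumption: the cited study was of court-referred women with alcohol and aggression problems, not veterans given MBSR.

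**Conclusion.** The point holds as a contradiction between two sections plus an open-ended rule. As written, the exclusion criterion conflicts with intent-to-treat. Under the rescheduling text, a participant who never screens negative contributes nothing to the TRT, HR, SC or DERS-S comparisons, and their post-treatment questionnaires and 3-month visit are delayed or may be lost for a reason that concerns only the laboratory tasks.

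A reader might go on to infer a demonstrated bias. The documents do not support that, since neither its size nor its direction can be derived from them. The 0.05 to 0.08 SD figure rests wholly on the assumed 20% versus 10% permanent loss and 0.5 to 0.8 SD gap. The case for changing the text is that a stated rule goes wrong if followed and is cheap to correct.

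**What to change.** 1. Reconcile the two sections: take the post-treatment screen out of the Exclusion Criteria and state it as a condition for running the experimental portion only.
2. Collect the self-report battery on the scheduled date whatever the urine result, and reschedule only the experimental portion. State a window and what is recorded if that portion is never completed.
3. Time the 3-month visit from the scheduled end of the 8-week course, which is the same in both arms, and invite all randomised participants to both visits.
4. Keep all randomised participants in the intent-to-treat set. Report positive screens and missing TRT by arm, and add a sensitivity analysis for questionnaires completed with a positive screen.

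The handling of withdrawal symptoms stays as the plan states it.

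The cost is protocol wording and some self-report data from participants with a positive screen, which the sensitivity analysis addresses. Reminder calls and collateral contacts are already planned under the attrition strategies.
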